## RESEARCH PROTOCOL

**Specific Aim 1 - Pilot RCT:** To evaluate both PrEP initiation and adherence, we will use a two-stage randomization design. In Stage 1, we plan to enroll 130 MSW (65 per randomization arm to achieve N=104 completers for Stage 1; ~80% retention), who will be equally randomized to receive either the PrEPare for Work strength-based case management (SBCM) or standard of care (i.e., referrals only) to evaluate successful PrEP initiation. In Stage 2, those who initiate PrEP (n~44; ~80% in Stage 1 intervention arm and ~20% in Stage 1 comparison arm), regardless of their Stage 1 randomization condition, will then be equally randomized to the PrEPare for Work adherence intervention condition or standard of care comparison condition (22 per randomization arm to achieve N=40 completers for Stage 2; ~90% retention). While we are aware that there may be important differences that affect adherence in those who initiate PrEP without additional SBCM and those who received SBCM, we anticipate that randomization at the second stage will balance out potential confounding by level of motivation to initiate PrEP. See point of contact diagram below for specific details.

**Recruitment:** All participants will be identified by staff at Project Weber, our community partner organization and study site for this study, and will live in or participate in sex work in RI. In addition to identifying participants at the drop-in center, participants will be recruited from a variety of sources: (1) members of our recruitment/outreach team will actively recruit participants in the community via direct outreach at venues where we know sex workers solicit clients (such as bars, night/dance clubs, on the streets), (2) via the internet, by posting study related advertisements which may include a brief anonymous self-administered pre-eligibility assessment, (3) via direct engagement with internet escorts on the internet for which

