Overview of the PrEPare for Work PrEP Initiation and Adherence Intervention Package (see appendix for manual).

1. Stage 1: Strengths-based Case Management to facilitate integration into The Miriam Hospital PrEP Clinic. Following Stage 1 randomization, participants randomized into the intervention arm will be provided a case manager to support, facilitate, and assist in linkage to our established PrEP clinic at The Miriam Hospital and to facilitate initiation of, and obtaining, PrEP medications. This is comprised of facilitated strengths-based case management to assess barriers to initiation, to help navigate the PrEP medical care system and to support the participant and health care staff in meeting the challenges faced with obtaining PrEP medication (e.g., overcoming insurance barriers, or barriers with copays). This also includes facilitated integration into the PrEP clinic and obtaining their PrEP prescription through the clinic (refilled monthly).

A trained staff member will be based at Project Weber and will provide case management to all eligible participants interested in taking PrEP. Staff will receive training concerning the provision of case management services, including how to use past experiences with sex work as a tool for understanding, role modeling, outreach and engagement, ethical guidelines, such as confidentiality and professional boundaries, and administrative tasks (e.g., documentation).

2. Stage 2. Only participants who complete an initial visit at the PrEP clinic are clinically evaluated, receive a prescription for PrEP, and confirm their interest in using PrEP for HIV prevention will be randomized in Stage 2 to either the PrEPare for Work adherence training and counseling condition or the standard of care condition. All participants enrolled in Stage 2 will be offered a study cell phone to receive appointment reminders and, for participants randomized to the intervention, to receive daily adherence SMS text reminders (full description on page 6 under Adequacy of Protection of Risk). Participants may choose to decline the study cell phone and/or to participate in the daily adherence SMS text reminders (full description SMS text component page four Section B). For participants who decline and elect to use a personnel cell phone for study appointment reminders and/or daily adherence SMS text messages standard text messaging rates will apply and are not compensated for by the study.

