- B. *Component II. Daily SMS text messaging of personalized reminders to take PrEP as prescribed (“reminder cues”)*. As an optional component, we will send daily text messages to all participants randomized to the PrEPare for Work intervention condition, as reminders to take PrEP as prescribed and as cues regarding behavioral skills gained as a result of in person adherence counseling sessions. The messages will not have any information about the participant’s health, medication or any information identifying them as a MSW. Text messages will be programmed to begin upon completion of the stage two baseline and to end upon the completion of the three-month follow-up visit. Participation in text message reminders will be left to the participants’ discretion, may be deployed on a study cell phone or a personal cell phone, and can be stopped at any time. Text messages will be programmed utilizing a web-based data management system. This system is password protected and available only to trained study personnel. Text messages are registered by participant ID and study cell phone number. Participants personal information cannot be traced back to study cell phones. Participants electing to use personal cell phones to receive text reminders will be registered by name and phone number to eliminate identifying the study ID with a personal phone number.

**Data management:** Demographic and behavioral assessments will be administered primarily on a tablet computer using a web-based data collection tool system. As the participant enters data points, each response will be immediately encrypted and transmitted back to a secure server. This will enhance confidentiality and minimize risks to patients. The digital data collection tool will be programmed to automatically store identifiable information and any PHI in a separate database from questions about demographics, risk behaviors, and health outcomes. No data will be stored on the tablet computer at any time.

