**Exclusion criteria:**

- Unable to provide informed consent, including as a result of severe mental illness requiring immediate treatment or mental illness limiting the ability to participate
- HIV Positive at baseline
- Infected with Hepatitis B or diagnosed with renal insufficiency (glomerular filtration rate < 50) \*Stage 2
- History of or current medical conditions that would preclude taking Truvada for PrEP \*Stage 2
- Currently taking Truvada for PrEP

Sample size: We expect to recruit 130 participants for the pilot RCT (Specific Aim 1).

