Statistical Analysis Plan

September 15, 2015

Optimizing PrEP Uptake & Adherence Among Male Sex Workers (MSW)
Using a 2-stage Randomization Design
(NCT03086057)

Specific Aim 2: Pilot RCT. Initially, the distribution of all variables will be assessed, as will the autocorrelations across time between all study variables and the primary outcomes. Dependent variables will be examined to determine which distributional models are most appropriate for subsequent statistical procedures. We will examine the equivalence of the random assignment of groups with regards to key baseline characteristics, including socio-demographics and sexual risk-related variables. In the unlikely event that randomization does not work to balance these characteristics at baseline, we will assess whether baseline differences may account for differences in outcomes. Attrition effects will be evaluated by testing whether systematic differences exist between those participants who complete the research versus those who drop out. In this way, we can determine the nature of the potential bias introduced by attrition from the study.

Primary Analysis. The primary analysis for Stage 1 will compare PrEP initiation at 1-month post Stage 1 randomization between the study arms. For stage 2, the primary analysis will compare adherence (defined by percent of drug in blood) at the 3 and 6 month visits between the study arms. Changes in self-reported adherence, sexual behavior adjustment and substance use will also be examined. Moreover, group differences in number of PrEP clinic appointments kept will be compared. All analyses will use two-tailed tests of significance, with significance at alpha = 0.05. We will use generalized linear models (GLM) with properly-chosen link functions to analyze longitudinal data for each analysis. The GLMs will be estimated using generalized estimating equations with robust standard error estimates (GEE)^{67,68}, which provides an extension of regression analysis to the case of correlated or repeated observations and allows for inclusion of both categorical and count dependent variables and for appropriate modeling of covariance structures when observations are correlated across time. We will follow an intent-to-treat model, analyzing participants in the study arm to which they were assigned, regardless of fidelity to assigned group.

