Power and Sample Size Considerations. As a pilot study, the primary emphasis is on feasibility of the two arms and hence power is limited; and to find statistical significance, the effect sizes would need to be large. However, the number of repeated measures does increase power for the longitudinal analyses. For stage 1, proportion of participants in each condition who initiate PrEP, with a two-tailed p-value of 0.05, and 53 participants per arm, we would need at least a 30 percentage point difference across the two conditions (e.g., if 20% of the comparison arm and 50% of the intervention arm initiated PrEP) to achieve 80% power. For stage 2, percent adherence since the last visit will be assessed yielding 3 repeated blood-drug levels across baseline, 3, and 6. With a two-tailed p-value of 0.05, group sample sizes of 22 participants per arm, assuming a correlation of 0.80 between repeated adherence measures and with up to 10% attrition there will be greater than 80% power to detect in excess of a medium effect size difference (approximately 10% in the slope) between the intervention and comparison groups. For categorical outcomes (e.g. percent of patients in each condition achieving at least 90% adherence via blood drug levels), with a two-tailed p-value of 0.05, the three repeated measures, and 22 patients per arm, we would need at least a 25 percentage point difference across the two conditions (e.g., if 50% of the comparison arm and 75% of the intervention arm had at least 90% adherence) to achieve 80% power.

Missing Data. We will assess for patterns of missing data, which are expected to be low as the study utilizes A-CASI. We will explore strategies for imputing missing data based on patterns of missingness and apply appropriate techniques, applying sensitivity analysis to determine the optimal method of handling the missingness⁷¹⁻⁷³.

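### The SAP's Stage 2 power text treats one blood drug level per visit as percent adherence over the preceding interval, and counts baseline, where that quantity is undefined, as one of three measures

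*SAP*

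**What the plan says.** The SAP describes the Stage 2 outcome in three ways.

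- Primary Analysis: the comparison is of "adherence (defined by percent of drug in blood) at the 3 and 6 month visits". Baseline is not named.
- Power and Sample Size Considerations, continuous measure: "percent adherence since the last visit will be assessed yielding 3 repeated blood-drug levels across baseline, 3, and 6". Here baseline is one of three measures, and the effect is stated as a difference in slope.
- The same section, binary measure: "percent of patients in each condition achieving at least 90% adherence via blood drug levels", again with three repeated measures.

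Neither document names the blood matrix, the analyte or the look-back window, or gives a rule for turning a concentration into a percentage or into the 90% category.

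On who reaches the Stage 2 baseline, the protocol's exclusion criteria list "Currently taking Truvada for PrEP". The Stage 2 paragraph of the intervention overview says that participants who "are clinically evaluated, receive a prescription for PrEP, and confirm their interest in using PrEP for HIV prevention will be randomized in Stage 2"; no dose need have been taken. The Specific Aim 1 paragraph speaks instead of "those who initiate PrEP (n~44; ~80% in Stage 1 intervention arm and ~20% in Stage 1 comparison arm". No section fixes the time from first dose to the Stage 2 baseline.

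The protocol also collects hair for drug levels (Study Sites; Research Assessments), and a phone follow-up yields hair but no blood. The SAP does not mention hair.

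**The concern.** A blood level is a concentration at one moment. The share of doses taken since a visit about 90 days earlier is a different quantity, and the power section treats the two as the same. Two things follow if the text is applied as it stands.

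First, a percentage for a whole visit interval would be attached to a measure that, under ordinary accumulation and decay, depends mostly on the later part of that interval. A late lapse or a late improvement would be read as the pattern of the full three months.

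Second, a value taken before the intervention, which reflects time on drug as well as adherence, would enter the slope, the 90% outcome and the power calculation as though it were an adherence result. The slope and the assumed correlation of 0.80 both depend on that value. This is the Stage 2 primary outcome, and any conversion or cut-off not fixed now would have to be chosen after data are in hand.

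**Working it through.** **Inputs.** From the SAP power section: 22 per arm, two-sided 0.05, correlation 0.80, up to 10% attrition (22 × 0.9 = 19.8, about 20 per arm), and 50% vs 75% for the binary outcome. Visits are at baseline, 3 and 6 months, so the interval is about 90 days. Assumed, because the documents do not give them: half-life h of 1 to 17 days, first-order accumulation with daily dosing, and compound symmetry.

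**1. The plan's own figure.** The detectable difference in SD units at 80% power is (1.960 + 0.842) × √(2f/n), where f is the variance factor. For the slope over three equally spaced visits, expressed as total change from baseline to month 6, f = 2(1 − 0.80) = 0.40.

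- n = 20: 2.802 × √(0.80/20) = 2.802 × 0.200 = 0.56 SD.
- n = 22: 0.53 SD.

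This agrees with the claim of somewhat more than a medium effect, if medium means 0.5 SD. The accompanying 10% cannot be checked because no SD is given. It implies an SD of about 18 points if it is the six-month change (10/0.56), or about 36 points if it is per three-month step (10/0.28).

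**2. What a level weights.** A dose taken d days ago has weight 2^(−d/h). As a share of the full steady-state level, the last 30 days contribute 1 − 2^(−30/h), and the 60 days before them contribute 2^(−30/h) − 2^(−90/h).

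| | h = 1 day | h = 17 days |
|---|---|---|
| Last 30 days | 1.00 | 0.706 |
| First 60 of 90 days (67% of the interval) | 0.00 | 0.269 |
| 20% of doses for 60 days, then all for 30 (true 47%) | 1.00 | 0.2 × 0.269 + 0.706 = 0.76 |
| All doses for 60 days, then none (true 67%) | 0.00 | 0.27 |

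The last two rows count only doses within the 90 days. A longer half-life does not restore equality. At h = 60 days, the last 30 days carry 29%, the previous 60 days 35%, and 35% comes from before the interval. Under this model no half-life gives equal weights confined to the time since the last visit.

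**3. Baseline.** For a fully adherent participant t days after the first dose, the level is 1 − 2^(−t/h) of steady state.

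- h = 17: 0.25 at 7 days and 0.71 at 30 days.
- h = 1: 0.99 at 7 days.
- No dose yet: zero at any half-life.

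Unless the half-life is very short, the reading varies with time on drug even when adherence is perfect, and that time is not fixed.

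**4. Power with two post-baseline measures.** For the mean of months 3 and 6, f = (1 + 0.80)/2 = 0.90.

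- n = 20: 2.802 × √(1.80/20) = 2.802 × 0.300 = 0.84 SD (0.80 SD with 22).
- Power at 0.56 SD with 20 per arm: Φ(0.56/0.300 − 1.960) = about 46%, against 80% for the slope.

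Binary outcome, 50% vs 75%, 22 per arm: effective n = 22/0.90 = 24.4. Power = Φ[(0.25√24.4 − 1.960√(2 × 0.625 × 0.375)) / √(0.25 + 0.1875)] = Φ(−0.16) = about 44%. With three measures at the same correlation, f = 0.867 and power is 45%; with three independent measures it is 85%. The stated 80% for this outcome is therefore not reached at correlation 0.80 even with baseline included. That is a separate matter.

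**The case against.** The strongest reply is that the interval phrase occurs only in the power section. The Primary Analysis names months 3 and 6, claims no three-month look-back and does not use baseline as a comparison time. That is correct, and it confines the baseline problem mainly to the slope, the 90% outcome and the power text. It does not remove the conflict between the two sections.

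Randomization also protects the comparison: a difference between arms in blood level is a valid difference in blood level. This stands. The fault lies in what the level is called and what it is said to show.

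Three stronger readings are tempting, and the documents do not support them.

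- A reader might infer that blood can show only recent dosing and can never inform a three-month figure. With no assay, half-life or window stated, the supportable statement is that the link is undefined and that, under first-order decay, a level weights recent doses most.
- A reader might infer that the baseline level carries no information about adherence. Some participants may have been dosing for weeks, since one paragraph refers to initiation and Stage 1 has one- and two-month visits; with a short half-life a level soon approaches steady state. The problem is unequal and unrecorded exposure.
- A reader might infer that the error favours the intervention arm at month 3 because reminders are active then. The protocol says "Text messages will be programmed to begin upon completion of the stage two baseline and to end upon the completion of the three-month follow-up visit". Reminders therefore cover the whole interval, early days as well as late ones. They are also optional and part of the intervention under test.

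Finally, using the baseline level as a covariate would recover precision. With a correlation of 0.80 to follow-up, f = 0.90 − 0.64 = 0.26, giving 0.45 SD with 20 per arm. That correlation cannot be taken for granted when the baseline reading partly reflects time since first dose.

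**Conclusion.** The concern holds in a limited form. The power section equates a level at one time with a percentage over an interval, includes a baseline value for which that percentage is undefined, and disagrees with the Primary Analysis on which visits count.

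Under the assumed half-lives of 1 to 17 days, the first two thirds of an interval supply 0% to 27% of the steady-state level. True adherence of 47% can read as 76% to 100%, and 67% as 0% to 27%. Without baseline as an outcome, the detectable difference rises from 0.56 to 0.84 SD (compound symmetry, correlation 0.80, 20 per arm, no covariate adjustment). The half-lives and the correlation structure are assumptions; the conflict between the sections and the undefined baseline do not depend on them.

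It is not shown that the comparison between arms is biased or that the assay is unsuitable. For a pilot centred on feasibility, this is a correction that should be made before analysis; it does not undermine the design.

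**What to change.** 1. In both Primary Analysis and Power and Sample Size Considerations, define the Stage 2 primary outcome as the blood drug level at months 3 and 6, or a category of it with a pre-stated cut-off. Name the matrix, the analyte and the dosing window, and limit the conclusion to that window. Give the 90% outcome an explicit definition in terms of the level, or remove it.
2. Do not count the Stage 2 baseline level as an adherence outcome in the slope or in the 90% outcome. Record days since first dose and report the two together descriptively.
3. Report the hair level and self-reported adherence, both already planned, beside the blood result. Claim the full interval from them only if their stated window covers it. State how follow-ups with hair but no blood are handled.
4. Restate the Stage 2 power for two post-baseline measures with an explicit SD: about 0.84 SD detectable with 20 per arm, and about 44% power for 50% vs 75% with 22 per arm, at correlation 0.80.

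The work is SAP wording, one recorded date and an added table; no new samples are needed. The price is a narrower primary claim and a less favourable power statement.

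### Stage 2 power is stated for a slope that the primary analysis does not name; at the SAP's own correlation the detectable difference runs from about 0.46 to 0.86 SD, depending on an unstated use of baseline

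*SAP*

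**What the plan says.** The SAP's Primary Analysis section defines the Stage 2 comparison: "the primary analysis will compare adherence (defined by percent of drug in blood) at the 3 and 6 month visits between the study arms". The model is a GLM fitted by GEE with robust standard errors. No slope, time-by-arm term or baseline drug level is mentioned. Baseline characteristics appear only in a balance check, with a follow-up assessment if the arms differ.

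The Power and Sample Size Considerations section describes the Stage 2 data differently: "percent adherence since the last visit will be assessed yielding 3 repeated blood-drug levels across baseline, 3, and 6". With 22 per arm and "assuming a correlation of 0.80 between repeated adherence measures and with up to 10% attrition", it claims "greater than 80% power to detect in excess of a medium effect size difference (approximately 10% in the slope". It gives no SD. Earlier in the same paragraph it concedes that power is limited and that only large effects would reach significance, then adds: "However, the number of repeated measures does increase power for the longitudinal analyses".

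Two parts of the protocol bear on how informative a baseline level can be. The exclusion criteria list "Currently taking Truvada for PrEP". The Stage 2 item of the intervention overview says that participants who complete a first clinic visit "are clinically evaluated, receive a prescription for PrEP, and confirm their interest in using PrEP for HIV prevention will be randomized in Stage 2". Specific Aim 1 puts entry slightly differently: "In Stage 2, those who initiate PrEP". Neither document says when the Stage 2 baseline sample is drawn relative to the first dose.

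**The concern.** A slope over three visits and a comparison at two follow-up visits are different contrasts with different variances. The slope uses each participant's baseline as a reference, so a high correlation shrinks its variance. A mean of two follow-up visits without baseline works the other way: high correlation makes the second visit nearly redundant. Power worked out for one does not carry over to the other.

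What is at stake is how the pilot's Stage 2 result is read and reused. Anyone judging a null result, or planning a later trial from it, would naturally attach the stated power to the named primary comparison. Whether that is too generous or too cautious depends on a modelling choice that the SAP does not record.

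**Working it through.** **Inputs.** Two-sided alpha 0.05 (SAP, Primary Analysis). 22 per arm, up to 10% attrition, correlation 0.80 (SAP, Power and Sample Size Considerations). 40 completers, so 20 per arm (protocol, Specific Aim 1; 22 × 0.9 = 19.8).

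**Assumptions.** SD of 1 at every visit; the same correlation r for all pairs unless stated; months 3 and 6 averaged, which the SAP does not specify.

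**Method.** SE = √(2V/20), where V is the per-participant variance of the contrast. By noncentral t, 80% power needs a difference of 2.875 SE on 38 df, or 2.877 SE on 37 df with a covariate.

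**The SAP's figure first.** The least-squares slope over 0, 3 and 6 months depends only on the month 6 minus baseline change, with V = 2(1 − r) = 0.40. SE = √0.04 = 0.20, and 2.875 × 0.20 = 0.575 SD. Taking medium as 0.5 SD (an assumption), this fits an effect in excess of medium. At exactly 0.5 SD the slope's power is 68%. With no SD given, the 10% itself cannot be checked.

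**The months 3 and 6 mean at r = 0.80.**
- Baseline unused: V = (1 + r)/2 = 0.90; SE = 0.30; 2.875 × 0.30 = 0.862 SD.
- Baseline as covariate: V = 0.90 − 0.80² = 0.26; SE = 0.161; 2.877 × 0.161 = 0.464 SD.

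The SAP's slope lies between the two.

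**Dependence on the 0.80.** Under one common correlation, 20 per arm:

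| r | Slope (SD) | Months 3/6 mean, no baseline (SD) |
|---|---|---|
| 0.5 | 0.909 | 0.787 |
| 0.6 | 0.813 | 0.813 |
| 0.7 | 0.704 | 0.838 |
| 0.8 | 0.575 | 0.862 |
| 0.9 | 0.407 | 0.886 |

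The two contrasts tie at 0.6 and the order reverses below it.

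**An uninformative baseline.** If baseline levels are near zero for everyone, month 6 minus baseline is in effect the month 6 level. Then V = 1, SE = √0.1 = 0.316, and the slope needs 0.909 SD.

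**Baseline as covariate, correlation b with each follow-up visit, months 3 to 6 held at 0.80.** V = 0.90 − b²:

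| b | V | Detectable (SD) |
|---|---|---|
| 0.3 | 0.81 | 0.82 |
| 0.5 | 0.65 | 0.73 |
| 0.7 | 0.41 | 0.58 |
| 0.8 | 0.26 | 0.46 |

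**Power at the back-solved 0.575 SD, same effect at both visits.** Without baseline, 0.575/0.30 = 1.92 SE and power is 46%. With a covariate at 0.80, power is 93%. If the arms instead diverge linearly to 0.575 SD at month 6, the average effect is 0.75 × 0.575 = 0.43 SD and power without baseline is 29%.

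**Percentage points.** If the 10% means 10 points by month 6, 0.575 SD implies an SD of 10/0.575 = 17.4, and 0.862 SD is 15 points. If it means 10 points per visit interval, the SD is 20/0.575 = 34.8, and 0.862 SD is 30 points.

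**The case against.** The strongest reply is that a GEE on all three drug levels, or one with a baseline covariate, fits the SAP's wording. The plan calls the data longitudinal, allows for correlation over time and counts three measurements; months 3 and 6 may simply name the follow-up visits. This stands. A reader might infer that the primary analysis omits baseline, but the documents are only silent on it. With baseline as a covariate at 0.80, the SAP's claim is conservative.

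A reader might also infer that true Stage 2 power is 46% rather than above 80%. The documents do not support that. The 46% needs baseline to be left out, an effect back-solved from a claim without an SD, and a constant effect at both visits. It is illustrative only.

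The gap also depends on the 0.80, as the common-correlation table shows. This does not rescue the stated claim: at 0.6 the slope needs 0.81 SD, well above what the SAP implies. Nor is 0.80 with baseline justified anywhere, given that current users are excluded and Stage 2 follows a new prescription.

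Finally, the SAP calls itself a pilot with limited power and says effects would need to be large. That is fair disclosure, and 0.86 SD is large. It limits the severity, but the sentence on repeated measures then qualifies the caveat for this very analysis.

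**Conclusion.** The mismatch is in the text: power is stated for a slope, and the primary comparison is at months 3 and 6. At 20 completers per arm and correlation 0.80, the primary comparison could detect anything from about 0.46 SD (baseline as covariate) to about 0.86 SD (baseline unused), against 0.575 SD for the slope. The direction of the error is therefore undetermined. If baseline is near zero for everyone, the stated claim fails on its own terms, since the slope then needs about 0.91 SD.

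These figures rest on equal SDs across visits and on averaging the two follow-up visits. The wording mismatch is certain; which figure applies is not. This is a minor error of power justification. It introduces no bias and leaves the feasibility aims and enrolment untouched.

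**What to change.** In the SAP:

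1. Name the Stage 2 primary contrast as the arm difference in blood drug level over months 3 and 6, and say whether the two visits are averaged or tested separately.
2. Include the Stage 2 baseline drug level, already part of the planned measurements, as a covariate, or use a longitudinal model with the arms constrained equal at baseline. State when that sample is drawn relative to the first dose.
3. Replace the slope-based power sentence with the detectable effect for this contrast at 20 per arm: 0.86 SD if baseline is unused or uninformative; as covariate, 0.82, 0.73, 0.58 and 0.46 SD at baseline correlations of 0.3, 0.5, 0.7 and 0.8.
4. Give the SD used to convert these to percent adherence.

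The cost is a few sentences, with no change to design or enrolment. The downside is a less favourable stated figure unless a strong baseline correlation can be justified.

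### The Stage 2 categorical power claim (80% for 50% vs 75%, 22 per arm) needs three nearly uncorrelated measures that all carry the arm difference; at correlations of 0.59 to 0.80 power is about 40-52%

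*SAP*

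**What the plan says.** The categorical calculation is the last power statement in the SAP's Power and Sample Size Considerations. Its conditions are "with a two-tailed p-value of 0.05, the three repeated measures, and 22 patients per arm", and its conclusion is "we would need at least a 25 percentage point difference across the two conditions" for 80% power, illustrated by 50% and 75% of patients reaching at least 90% adherence by blood drug level. The sentence mentions neither correlation nor attrition.

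Four other statements bear on it:

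- The preceding sentence, on continuous percent adherence, is the only place where a correlation appears: "assuming a correlation of 0.80 between repeated adherence measures and with up to 10% attrition".
- The same paragraph identifies the three measures: "yielding 3 repeated blood-drug levels across baseline, 3, and 6".
- The SAP's Primary Analysis compares adherence "at the 3 and 6 month visits between the study arms", using GEE with robust standard errors.
- The protocol (Specific Aim 1) plans "22 per randomization arm to achieve N=40 completers for Stage 2; ~90% retention", which is 20 completers per arm. In its Stage 2 description, "Text messages will be programmed to begin upon completion of the stage two baseline", and counselling sessions are scheduled only after assignment.

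**The concern.** Repeated measures on one person add information to a between-arm comparison only to the extent that they are not correlated. The SAP assumes a strong correlation (0.80) for the continuous drug level and then, for a cut of that same drug level, gives a figure that works only with almost none. It also counts the baseline as one of three informative measures, although the Stage 2 intervention has not begun by then and no arm difference is expected.

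A reader would take 25 points as detectable with 80% power. If the true figure is about half to two-thirds of that, a non-significant categorical result could be given more weight as evidence of no effect than it deserves.

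**Working it through.** **Inputs.** Two-sided alpha 0.05, p1 = 0.50, p2 = 0.75, n = 22 per arm and k = 3 measures (SAP, categorical sentence); 20 completers per arm (protocol, Specific Aim 1); k = 2 if only months 3 and 6 carry the difference (SAP, Primary Analysis). The correlation rho is not stated for this outcome, so a range is shown.

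**Formulas.** Pooled two-proportion z test:

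power = Φ{ [ |p2 − p1|·√n − 1.96·√(2·p̄(1 − p̄)) ] / √(p1(1 − p1) + p2(1 − p2)) }, with p̄ = 0.625.

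For a time-averaged between-arm difference with exchangeable correlation, n is replaced by n_eff = n·k / (1 + (k − 1)·rho).

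**Reproducing the stated figure.** The two square-root terms are √0.46875 = 0.6847 and √0.4375 = 0.6614. The n for 80% power is [(1.96 × 0.6847 + 0.8416 × 0.6614) / 0.25]² = 57.7, so 58 per arm (57 gives 79.5%, 58 gives 80.2%). With a continuity correction the requirement is 66, which is exactly 22 × 3. That fits a calculation in which three measures counted as three patients, though the SAP does not say so. A single measure on 22 patients per arm gives 39.9%.

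**Correlation needed for 80%.** With three measures:

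- 22 per arm: (66/57.7 − 1)/2 = 0.07.
- 20 per arm: (60/57.7 − 1)/2 = 0.02.

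With two measures, n_eff is at most 44 (22 per arm) or 40 (20 per arm). Both are below 58, so no correlation from 0 to 1 gives 80%.

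**Power for 50% vs 75%.**

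| rho | 22/arm, k=3 | 20/arm, k=3 | 22/arm, k=2 | 20/arm, k=2 |
|---|---|---|---|---|
| 0 | 85.1% | 81.6% | 68.4% | 64.1% |
| 0.2 | 71.4% | 67.2% | 60.3% | 56.1% |
| 0.5 | 55.7% | 51.7% | 50.7% | 46.9% |
| 0.59 | 52.0% | 48.2% | 48.4% | 44.7% |
| 0.80 | 45.0% | 41.6% | 43.6% | 40.2% |

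The value 0.59 is derived, not stated in the documents. If 0.80 is the correlation of an underlying normal drug level, cutting that level at its median gives a binary correlation of 0.590 (0.568 for a cut at 75% prevalence).

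**Difference from 50% needed for 80% power.**

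| rho | 22/arm, k=3 | 22/arm, k=2 | 20/arm, k=2 |
|---|---|---|---|
| 0.59 | 33.3 points | 34.6 points | 36.0 points |
| 0.80 | 35.9 points | 36.4 points | 37.9 points |

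**Check by simulation.** With dichotomised normal data at latent correlation 0.80 and a logit arm effect with cluster-robust standard errors (20,000 runs), power was 45.9% (20 per arm, k=2) and 53.2% (22 per arm, k=3). Type I error was 5.1-5.4%. The closed-form values at rho 0.59 are 44.7% and 52.0%.

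**The case against.** **The result depends on the model.** The SAP does not say how the Stage 2 baseline enters the GEE, and the preceding power sentence speaks of a slope, so a baseline-adjusted or change analysis is a plausible reading. Simulation with 50% vs 75% at both follow-ups, 50% at baseline in both arms and latent correlation 0.80 gives about 64-68% for a baseline-adjusted linear comparison and about 47-50% for change from baseline (20 and 22 per arm). The adjusted figure is clearly above 40-52% but still short of 80%. It also needs an informative baseline, which is doubtful when current PrEP users are excluded and Stage 2 follows a new prescription. Entering 0.80 directly as the binary correlation in a baseline-adjusted formula would exceed 80%, but that correlation cannot occur between margins of 50% and 75%: the maximum is √(0.25/0.75) = 0.58.

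**The 40% end stacks assumptions.** It combines 10% attrition, two visits, and 0.80 applied directly to the binary outcome. That is true. The most favourable corner at rho 0.59 (no attrition, all three measures carrying the difference) is still only 52%.

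**Little depends on the sentence.** The SAP says that pilot power is limited and effects would need to be large. The outcome is an example, the primary Stage 2 outcome is percent of drug in blood, and 22 per arm comes from the expected number of initiators. All this limits the harm, but a general caveat does not correct a specific number.

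**Conclusion.** The concern holds. The stated 80% can be reproduced only by treating three measures per patient as almost independent and letting the baseline carry an arm difference. For the between-arm comparison the SAP describes, power for 50% vs 75% is about 40-52% at correlations of 0.59 to 0.80, and 80% power needs about 33-38 points instead of 25. If only months 3 and 6 contribute, the ranges narrow to about 40-48% and 35-38 points.

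These ranges assume an unadjusted time-averaged contrast and exchangeable correlation, and the correlation values are assumptions. That the 80% is unsupported as written is firmer than any single replacement figure: the baseline-adjusted and change-from-baseline alternatives simulated also fall short. This should be fixed, but no sample size, endpoint or decision rule depends on it.

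**What to change.** In the SAP's Power and Sample Size Considerations, state for the categorical outcome the within-person correlation, the visits that carry the arm difference, the attrition and the analysis model. Remove the claim that three repeated measures give 80% power at 25 points, and restate the figure to match.

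Possible wording, if months 3 and 6 are the visits compared: *With 20-22 patients per arm, two follow-up visits and an assumed correlation of about 0.6-0.8 between the repeated categorical measures, power for 50% vs 75% is about 40-48%, and 80% power requires a difference of about 35-38 points.* If all three measures are meant to count, the corresponding figures are about 42-52% and 33-37 points, and the SAP should explain why the baseline would differ by arm. If a baseline-adjusted model was intended, name it and show its assumptions, including the expected baseline prevalence.

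The cost is a wording change and a less favourable stated figure. No extra participants are needed, and no endpoint or test changes.
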